4.1 Inclusion Criteria

Subjects must meet all of the following inclusion criteria:

1. Males and females aged 9 months to 9y0m0d at the time of consent.
2. Able to obtain parental or legal guardian written informed consent from subjects as applicable by local laws and regulations.
3. Subjects must have a G or G/J tube.
4. Subjects must receive over 80% of their total daily calorie needs from a tube in order to be classified as tube dependent.
5. Subjects must have a ≥ 3 month history of feeding problems as identified by a diagnosis from a multidisciplinary feeding team, and must have permission from the physician on the team to ensure that they are medically stable enough to participate in a weaning study. (*Please refer to Medically Stable Screening Form to help guide assessment*).
6. Subjects must possess the oral motor skills necessary for eating according to Table 1 in the Appendix.
7. Subjects must possess behavioral skills necessary for mealtime according to Table 2 in the Appendix, or be judged by the professionals on the feeding team as able to meet these behavioral skills by week 10 of the protocol.

4.2 Exclusion Criteria

Study enrollment will exclude potential subjects with any of the following conditions or taking any of the following medication:

1. Children receiving oral steroids.
2. Parent has a known developmental delay or cognitive impairment that may make participation in the study difficult (children with these issues will not be excluded).
3. Children receiving intensive (defined as more than one session per month) behavioral feeding therapy with a licensed psychologist (previous behavioral feeding therapy is not an exclusion criterion; neither is current oral-motor, sensory, or speech therapy).
4. Children of non-English speaking parents.

CONFIDENTIAL

This material is strictly confidential and is intended solely for the guidance of clinical investigation. Do not disclose or use except as authorized in writing by the study sponsor

4.3 Subject Recruitment and Screening

Sixty subjects are needed for our analysis plan, so with a maximum of 20% drop out (which exceeds drop out from our previous work), a total sample of 72 will need to be recruited over the 5 year project (for more information see Sample Size Determination in Data Analysis Plan section). To allow for study start up and completion phases, we will need to recruit approximately 20 subjects per year when in active recruitment. Currently, the University of Kansas Medical Center team sees 12 new patients per month, Children's Mercy Hospital sees 12 new patients per month, University of California San Diego/Rady Children's Hospital sees 8 new patients per month, the New Orleans site sees 8 new patients per month, Arnold Palmer Hospital for Children sees 8 new patients per month, and Children's Hospital of Philadelphia sees 12 new patients per month, resulting in a total potential recruitment base of 60 feeding subjects per month across our primary sites. Based upon clinic data, 20% of the patients seen will meet inclusion/exclusion criteria (resulting in 12/month or 144/year). Of these, we predict that half will be given permission to participate, given the highly medically complex nature of many children with feeding problems (resulting in 72/year). Assuming that half of eligible families participate (36/year), current clinic volume at participating sites will result in successfully meeting recruitment goals.

Participants will be recruited by a pediatric healthcare provider or other members of the feeding team at each site. Sites will likely recruit through their multidisciplinary feeding teams, but may recruit from other clinics, patient registries, electronic medical records, and inpatient settings as appropriate. Methods of recruitment could include: approaching patients during routinely scheduled patient visits, sending letters, emails, or calling patients identified through an electronic medical record or other site specific patient registry, or emailing patients through the electronic medical record platform. Sites may also place recruitment flyers, informational videos, and information on their institution's local webpage or social media pages, affiliated research network pages (such as Pioneers Research Network at KUMC or other affiliated research center websites), post ads to social media and local media, and post flyers in the community or to online groups (such as social media or other sites that focus on feeding issues in children, parents of tube-fed children, etc.) If parents are interested in participating, they will have access to a toll free number to call with questions, or they may request to be contacted by entering their contact information in a REDCap survey. Our team members are experienced with each of these types of recruitment methods and many were used in our previously funded NIH study in feeding.

4.4 Early Withdrawal of Subjects

4.4.1 When and How to Withdraw Subjects

Subjects will be considered "at risk" and reviewed by the medical monitor and site PI if either of the following two conditions. The medical monitor and site PI will determine if it is safe for the participant to continue in the study (or, under what conditions it may be safe for the participant to continue) given all patient characteristics, including baseline weight for height ratio or BMI percentile.

- 1) If more than 0.5 kg of weight is lost consistently per week over three consecutive weeks
- 2) If the subject experiences 10% loss of total body weight

Children who are removed from the study will be treated clinically.

4.4.2 Data Collection and Follow-up for Withdrawn Subjects

If a subject withdraws from the study, they will be asked to continue on with their assessments (at least height and weight and diet recall, at the very minimum). This will be done so we can have outcome on our primary endpoint even for subjects who withdraw. Unless a subject/parent actively refuses, we will try to contact them for these assessments via phone and email and if this fails, we will attempt to reach them via certified letter at their last known address.

CONFIDENTIAL

This material is strictly confidential and is intended solely for the guidance of clinical investigation. Do not disclose or use except as authorized in writing by the study sponsor

5 Study Drug

5.1 Description

Megestrol

Megestrol is a steroid and progestational drug FDA approved for treating anorexia or weight loss in patients with acquired immunodeficiency syndrome. Its use in the current protocol is “off label” to stimulate appetite in tube-fed infants and toddlers who are weaning from tube feedings and learning to eat. The precise mechanism of action that leads to increased appetite and weight gain is unknown, but is probably related to megestrol’s glucocorticoid effect (41). Side effects of megestrol include suppression of the adrenal glands and new onset diabetes mellitus (41). These complications are minimized by limiting the duration of treatment to 6 weeks (41). Other side effects include heart failure, nausea and vomiting, edema, dyspnea, hyperglycemia, alopecia, hypertension, carpal tunnel syndrome, mood changes, malaise, asthenia, lethargy, sweating and rash (41). Megestrol’s safety and effectiveness have not been established in children. However, there are several pediatric trials with megestrol for anorexia or malnutrition (42-44). In a megestrol trial for children with cystic fibrosis, the youngest child treated was 6 months of age and treated with 10 mg megestrol/day (42). The proposed study will use megestrol 6 mg/kg/day in two doses because this dose has been effective and safe in two previous studies using megestrol to stimulate appetite in children transitioning from tube to oral feedings. (6,45). Megestrol will be dosed at 6 mg/kg/d at weeks 10-11, at 4 mg/kg/d at week 12, at 2 mg/kg/d at week 13, and fully tapered at the end of week 13. Megestrol is absorbed from the small bowel, so feeding it through the tube will be acceptable (41).

Placebo Group

Subjects randomized to the placebo protocol will receive a placebo syrup identical in taste and smell to megestrol at the same intervals as those in the megestrol group but the syrup will contain no active ingredients.

5.2 Treatment Regimen

Megestrol will be dosed based off their weight at the Week 10 visit, and dose will be rounded to the nearest 0.1 ml. Megestrol will be dosed at 6 mg/kg/d at weeks 10-11, at 4 mg/kg/d at week 12, at 2 mg/kg/d at week 13, and fully tapered at the end of week 13.

Equal doses will be taken twice daily. Subjects will be given instructions on when to take the medication and what to do if they miss a dose. If it has been < 6 hours since missing the dose, they should take the dose as soon as they remember. If it has been ≥ 6 hours since missing the dose, they should skip the dose. Subjects will be asked to document any skipped doses and report those to the study team at their next visit.

If a participant is removed from the study while taking the study drug, we will follow the drug tapering plan based on what day they are in the treatment regimen:

- Day 1-14 Drug can be stopped at current dose.
- Day 15-18 Continue 4 mg/kg for a total of 3 days. Decrease to 2 mg/kg for 3 days and then stop.
- Day 19-21 Decrease to 2 mg/kg for 3 days and then stop.
- Day 22-23 Continue 2 mg/kg for a total of 3 days and then stop.
- Day 24-28 Stop drug.

Regardless of when the drug is stopped, a morning cortisol lab value will be taken 5 days after the final dose of study drug.

CONFIDENTIAL

This material is strictly confidential and is intended solely for the guidance of clinical investigation. Do not disclose or use except as authorized in writing by the study sponsor

5.3 Method for Assigning Subjects to Treatment Groups

Patients will be randomized within each site at a 1:1 ratio into the treatment and placebo groups. The statistician will generate ten sets of randomization codes, and send one set of codes to the pharmacist of each site. All the other study personnel will be blinded to the result of randomization.

Preparation and Administration of Study Drug

The pharmacy at each site will prepare megestrol or placebo for each subject as dictated by the random codes prepared by the study statistician. The compound formula for each site will be identical, and the taste, look and smell of the placebo and megestrol will be matched.

Subject Compliance Monitoring

Subjects will be asked to report missed doses of study medication during their regularly scheduled clinic or tele-visits. If a patient is significantly noncompliant with medication (as evidenced by missing 7 or more days of dosage in a one month period) subjects will be counseled, and withdrawn from the study if unable to change.

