3.4 Primary Safety Endpoints

Safety Interviews

To monitor for negative side effects, patients will be interviewed during clinic visits and tele-visits for any negative gastrointestinal, behavioral, feeding, or other negative sequela suspected to result from our treatment. Participants will be asked to measure the child's weight using a digital home weight scale during tele-visits to monitor changes in weight.

Subjects will be considered “at risk” and reviewed by the medical monitor and site PI if either of the following two conditions. The medical monitor and site PI will determine if it is safe for the participant to continue in the study (or, under what conditions it may be safe for the participant to continue) given all patient characteristics, including baseline weight for height ratio or BMI percentile.

- 1) If more than 0.5 kg of weight is lost consistently per week over three consecutive weeks
- 2) If the subject experiences 10% loss of total body weight

If any negative outcomes are identified they will be reported to our Data Safety and Monitoring Board and proper steps will be taken.

CONFIDENTIAL

This material is strictly confidential and is intended solely for the guidance of clinical investigation. Do not disclose or use except as authorized in writing by the study sponsor

Children will also have laboratory measurements to assess megestrol safety.

- 1) Morning Cortisol. The blood for the morning cortisol test will be drawn before 8am by the local laboratory or mobile phlebotomy services to test for adrenal insufficiency. The test will take approximately 1 mL of blood and will be drawn at weeks 10 and 14 for all subjects. Participants taking inhaled or intranasal steroids will take an additional blood draw at week 0. If an abnormal value is measured, a repeat morning cortisol level will be obtained. Every effort should be made to complete a redraw at the earliest convenience, within 7 days. The medical monitor will be on the weekly team calls, so she will be able to advise based on specific circumstances. If the 2nd test is also abnormal, the study protocol will be paused, and a pediatric endocrinologist will be consulted to determine if a formal in-person consultation is needed with endocrinology. The subject may either resume the protocol or be removed from the study pending the endocrinologist and study team's assessment.

4 Subject Selection and Withdrawal

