6.4 Clinic Visit 2 (Week 10)

Participants will return to clinic to complete vital signs and blood draw (morning cortisol). If an abnormal morning cortisol value is measured, follow the redraw procedures under section 3.4 Primary Safety Endpoints. Height and weight will both be taken in triplicate via calibrated equipment by a trained staff member. Participants will bring in a frozen stool sample. Patients will be given megestrol or placebo, but asked to wait to administer the 1st dose until lab value for morning cortisol are confirmed normal. Megestrol will be dosed at 6 mg/kg/d at weeks 10-11, at 4 mg/kg/d at week 12, at 2 mg/kg/d at week 13, and fully tapered at the end of week 13. Participants will be asked to complete the PIP, ITQOL or CHQ, RAND SF-36, PedsQL and schedule three 24 hr Dietary recall phone calls over the coming week. Five

CONFIDENTIAL

This material is strictly confidential and is intended solely for the guidance of clinical investigation. Do not disclose or use except as authorized in writing by the study sponsor

days after the clinic visit, parents will begin to taper G or G/J tube feedings by 10% each day until they are stopped altogether. Families will be encouraged to contact team members with questions or concerns at any time throughout the study period.

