patients will be contacted weekly while taking the medication (via the Tele-visits described previously) for any negative gastrointestinal, behavioral, feeding, or other negative sequelae suspected to result from the medications. (If such patients are subjected to stress such as an infection or surgery, they may develop adrenal crisis. The patient suddenly becomes cyanotic and cold, blood pressure drops, and without immediate resuscitation the patient goes into shock). If any negative outcomes are identified they will be reported to our Data Safety and Monitoring Board and proper steps will be taken.

Under certain conditions children may removed from the study and treated clinically. The medical monitor and site PI will assess the case and determine if it is safe for the participant to continue.

Risk/benefit assessment:

Our previous work suggests that iKanEat is effective in moving children from tube to oral eating, and that amitriptyline does not improve the outcomes associated with the protocol. However, we do not know if the remaining medication (megestrol) improves the outcomes associated with iKanEat. As all medications have risks, it is necessary to test this remaining medication to determine if the risk is outweighed by the benefit the medication brings to the iKanEat protocol.

Data Safety Monitoring Board

For the current study we will have a Data Safety Monitoring Board that will review all subject safety data twice annually. DSMB will review protocol adherence, adverse events, unanticipated problems, voluntary and study team initiated withdrawals, etc. This team is available to the investigators at any time should an issue of safety arise, as was the DSMB for their previous study (HD068221). This board will be composed of [name], Professor of Pediatrics and [name], Professor, Rady Children's Hospital and UCSD. Twice annual conference calls will be held between the DSMB members and the investigation team to assure the best outcome for all subjects. Any serious adverse events will be reported immediately to the relevant institutional IRBs and to the DSMB.

Population(s) for Analysis. Our primary analysis will focus on a protocol-compliant population, but we will secondarily also analyses the all-treated population, as described below.

- All-randomized population: Any subject randomized into the study, regardless of whether they received study drug

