- All-treated population: Any subject randomized into the study that received at least one dose of study drug
- Protocol-compliant population: Any subject who was randomized and received the protocol required study drug exposure and required protocol processing

8 Safety and Adverse Events

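### Persistent missed doses of the 4-week drug end a child's place in the 24-week study, and nothing provides for the iKanEat tele-visits to continue

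*Combined protocol and SAP*

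**What the plan says.** Megestrol or placebo is given for 4 weeks (weeks 10 to 13) inside a 24-week behavioural programme that both arms receive (Study Summary; section 5.2). For a child who misses seven or more days of dosing in a month, section 5.3 (Subject Compliance Monitoring) states that "subjects will be counseled, and withdrawn from the study if unable to change". It offers no option to stop the drug alone.

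Three provisions apply after withdrawal:

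- Section 4.4.2 says of withdrawing families that "they will be asked to continue on with their assessments (at least height and weight and diet recall, at the very minimum". The stated purpose is to obtain the primary endpoint.
- Section 4.4.1 says: "Children who are removed from the study will be treated clinically".
- Section 5.2 gives a taper table for a child removed while on study drug, and a cortisol draw 5 days after the last dose.

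None of these mentions the tele-visits.

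On analysis sets, section 7 says: "Our primary analysis will focus on a protocol-compliant population". That set is defined as "Any subject who was randomized and received the protocol required study drug exposure and required protocol processing". The all-treated set, which needs only one dose, is secondary.

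**The concern.** The drug is the short component and the behavioural programme is the long one. Under section 5.3, failing on the short one ends participation in the long one. Because the rule is applied blind, a child can be withdrawn for missing placebo.

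The interpretive cost falls on the all-treated analysis. A withdrawn child who took at least one dose belongs to that set, and section 4.4.2 seeks the week 24 diet recall. If the tele-visits stop at withdrawal, the outcome reflects two losses at once, the drug and the behavioural support. Only the first bears on Aim 1, which asks what megestrol adds to iKanEat. The fallback care is not the same thing. Section 6 has the tele-visits delivered by behavioural staff at the lead site, while section 3.3 (Other considerations) puts ordinary feeding-team visits typically 6 to 10 weeks apart.

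**Working it through.** The plan states no figure for this point, so there is none to reproduce. The check is a count of visits, a timeline, and the condition for bias.

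**Tele-visits scheduled (sections 6.3 to 6.10).** Weeks 1, 3, 5, 7, 9 (5), weeks 11, 12, 13 (3), week 14 (1), and weeks 15, 17, 19, 21, 23 (5). The total is 5 + 3 + 1 + 5 = 14, which agrees with the approximate count at the start of section 6.

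**Trigger.** Seven days of a 28-day course is 7/28 = 25%.

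**Earliest removal.** Take the week 10 visit as day 0, with contacts on days 7, 14, 21 and 28 (weeks 11 to 14). Parents are "asked to wait to administer the 1st dose until lab value for morning cortisol are confirmed normal". The turnaround is not given, so I assume the first dose falls on day L, with L between 1 and 7.

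- Seven whole missed days end no earlier than day L + 6, which is day 7 to day 13.
- The first contact after that is day 14 (week 12), when counselling takes place.
- Allowing one week to change (an assumption), removal comes no earlier than day 21 (week 13). Doses missed more gradually push it to week 14.

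**Tele-visits that may be lost.**

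| Removal at | Remaining tele-visits | Share of 14 |
|---|---|---|
| Week 13 | 14, 15, 17, 19, 21, 23 = 6 | 6/14 = 43% |
| Week 14 | 15, 17, 19, 21, 23 = 5 | 5/14 = 36% |

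**When the all-treated contrast is biased.** Work on the difference in success rates. Let w be the fraction of an arm withdrawn under section 5.3, and d the fall in success among those children caused by losing behavioural support. The arm's rate falls by w × d, so the difference, megestrol minus placebo, shifts by

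(w_placebo × d_placebo) − (w_megestrol × d_megestrol).

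This is zero when withdrawals and falls are equal in the two arms. Otherwise it can go either way. The documents give neither w nor d. The 20% drop-out allowance in section 4.3 is not split by reason. No size can therefore be derived.

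**Taper under a drug-only stop.** Day 21 is dosing day 21 − L + 1, which runs from 21 (L = 1) down to 15 (L = 7). The section 5.2 table requires a step-down on those days, but it is written for children removed from the study.

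**The case against.** The case against has real force.

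- Section 4.4.2 sets a minimum, so a site could keep the tele-visits going. This stands. The documents do not say either way, and that silence is what needs settling.
- The effect is on a secondary analysis, is conditional on a difference between arms, and cannot be sized. This stands, and it is why the point is minor.
- The rule can act only late in a 28-day course, so few children may be affected. This is plausible, though no rate is given.
- Withdrawal after counselling fits a protocol-compliant primary analysis. It does, but that analysis does not need the behavioural support to end.
- Section 5.4 lets the medical monitor handle study drug alone, but for steroid prescriptions lasting over 7 days, which is a safety matter. Agreed. It shows that drug-only handling is workable, not that section 5.3 contradicts it.
- The taper gap appears only once a drug-only stop exists. Agreed, so the two edits belong together.

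A reader might also infer a gap in weight safety, since children are weighed "using a digital home weight scale during tele-visits to monitor changes in weight". The documents do not support that. For removal at week 13, weights at weeks 10, 11, 12 and 13 plus the week 14 weight sought under section 4.4.2 give four consecutive weekly changes, covering the weeks 10 to 14 in which section 1.3 expects loss. The criterion "If more than 0.5 kg of weight is lost consistently per week over three consecutive weeks" has no stated starting point at the end of tube feeding. The 10% criterion can be judged at week 14. Both exist to decide whether a child may continue in the study.

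**Conclusion.** The point holds in a limited form. Section 5.3 ties a drug-adherence failure to leaving the whole study, and no section provides for the tele-visits afterwards. For a child with at least one dose removed at week 13 or 14, 6 or 5 of 14 tele-visits (43% or 36%) may be lost, and the all-treated week 24 outcome can mix the two losses. The timing rests on the assumed 1 to 7 day wait for the cortisol result and the one week allowed to change.

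Three stronger readings go too far:

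- That the primary result is distorted. The protocol-compliant set would normally exclude these children, and this point does not alter it.
- That week 24 data are lost. Section 4.4.2 seeks them.
- That removal could come earlier, with more visits lost. This needs a same-day start despite the cortisol wait and every dose missed. A child with no dose is outside the all-treated set.

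Cheap improvement, minor.

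**What to change.** In section 5.3, state that persistent non-adherence after counselling leads at most to stopping study drug, at the medical monitor's discretion. The child stays in all tele-visits, clinic visits and the week 14 and 24 assessments unless the family declines, and is analysed as randomised in the all-treated analysis.

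In section 5.2, extend the taper table and the 5-day cortisol check to any child who stops study drug early, whether or not the child leaves the study.

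The cost is a few sentences. The visits are already scheduled and no new data are collected. The downside is that a few poorly adherent families remain in scheduled visits.
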